9. APPENDICES

9.1 Main Intercurrent Events (ICE)

9.1.1 Immunosuppressants or dapsone at therapeutic doses for at least 4 weeks in total in the last 12 weeks before Week 36

- · Azathioprine, at least 1 mg/kg/day
- Mycophenolate mofetil, at least 2 g/day
- Mycophenolate mofetil hydrochloride, at least 2 g/day
- Mycophenolic acid, at least 1000 mg/day
- Cyclophosphamide, at least 1 mg/kg/day, or IV pulse 500 mg/month
- Methotrexate (sodium), at least 5 mg/week (in Japan), whereas 10 mg/week in Europe
- Ciclosporine, at least 3 mg/kg/day
- Dapsone, at least 1 mg/kg/day
- Hydroxychloroquine sulfate, at least 400mg/day
- Thalidomide, at least 50mg/day

For NCOD, time-to-event analyses and endpoints that consider the period 'through Week 36' any episode of at least 4 weeks in total is to be considered as an ICE, even if not in the last 12 weeks before Week 36. For these analyses, use the end of the 4 weeks as start date of the ICE. For endpoints 'at Week 36', use the end of 4 weeks that fully fall in the last 12 weeks before Week 36 as start date of the ICE.

SGS	Statistical Analysis Plan	
ARGX-113-2009	Final and Interim Analysis	Final 4.0 of 04NOV2024

9.1.2 IVIg/SCIg at immunomodulating dose (≥1 g/kg/month) at any moment before Week 36

'Immunoglobulins NOS' or 'Immunoglobulin G Human' or 'Immunoglobulins' or 'Immunoglobulin Human Normal' or 'Anti-D Immunoglobulin' and cmroute='INTRAVENOUS' or 'SUBCUTANEOUS'.

9.1.3 Immunoadsorption or plasma exchange (at least 1 procedure) at any moment before Week 36

• 'Plasmapheresis' or 'Immunoadsorption therapy' as PRDECOD, at least one cycle

9.1.4 Rituximab or other anti-CD20 biologics (at least 1 infusion) at any moment before Week 36

- Rituximab (PVVR, ARRX, ABBS), at least one cycle of 1 g or 375 mg/m²
- Obinutuzumab
- Ofatumumab
- Ocrelizumab
- Ibritumomab tiuxetan
- Veltuzumab
- Tocilizumab

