9.3.2. Primary Endpoint/Estimand Analysis

The estimand framework for analysis of the primary endpoint applies only to part B of this study.

- Population: adult participants with newly diagnosed or relapsing BP, regardless of whether the participant is naïve to treatment or has previously received treatment. Participants will be receiving concurrent therapy of oral prednisone (or equivalent OCS); therefore, candidates who have a known contraindication to OCS will be excluded from study participation (exclusion criterion 4).
- Variable: proportion of participants who are in CR while receiving efgartigimod PH20 SC or placebo and have been off OCS therapy for ≥8 weeks at week 36.
- Main intercurrent events (ICE):
 - 1. Intercurrent treatments before week 36
 - a. Immunosuppressants or dapsone at a therapeutic dose for at least 4 weeks
 - b. IVIg/SCIg at an immunomodulating dose (at least 1 g/kg/month)
 - c. Tetracyclines at therapeutic dose for at least 2 weeks
 - d. Rituximab or anti-CD20 biologic, at least 1 infusion
 - e. Plasma exchange or immunoadsorption, at least 1 procedure
 - f. IV or IM corticosteroids administered in the following conditions:
 - At least 1 administration, any dose, from week 28 to 36 (ie, during the 8-week period required to confirm CR off OCS therapy)
 - At any time before week 28 in any of the 3 following situations:
 - More than 60 mg/day of prednisone or prednisone equivalent dose for 3 consecutive days
 - More than 40 mg/day of prednisone or prednisone equivalent dose for 4 consecutive days
 - o More than 7 days in total
 - g. Any interventional study drugs under development for BP
 - h. Very potent TCS with a weekly dose >20 g for 1 week
 - 2. Discontinuation of IMP before week 36 due to lack of efficacy

Population-level summary: the odds ratio (95% confidence interval [CI]) under efgartigimod PH20 SC in combination with concurrent OCS therapy versus placebo in combination with concurrent OCS therapy.

Handling of main ICEs: a composite strategy approach will be taken to address both main ICEs. This implies that participants who take intercurrent treatments and participants who discontinue IMP due to lack of efficacy will be considered nonresponders for the primary endpoint analysis.

Handling of missing data:

- Missing data for reason of 1 of the main ICEs will be handled as described above.

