6. CHANGES TO THE PLANNED ANALYSIS

6.1 CHANGES NOT COVERED BY PROTOCOL AMENDMENTS BEFORE DATABASE LOCK

1.) The protocol specifies the NCOD calculation as:

Normalized cumulative OCS dose (NCOD) will be calculated normalized by weight and by number of days in study. The following formula will be adopted to calculate NCOD for each participant.

 $NCOD = \frac{\textit{Cumulative Dose of OCS from baseline to the week 36 visit}}{(\textit{Weight of the patient at baseline})} \times (\textit{number of days in study})$

Instead of the weight at baseline, it was chosen to use the most recent weight assessment instead. NCOD (mg/kg/day) is calculated for different periods as [the sum of (equivalent doses taking into account daily dose frequency)/(body weight in kg)]/(period duration in days) with body weight of visit closest before or at each start of prednisone equivalent medication instead of using weight at baseline.

- 2.) This SAP defines intercurrent medications in more detail than the protocol:
 - Immunosuppressants or dapsone at therapeutic doses for at least 4 weeks:
 - Doses considered as therapeutic dose are specified in SAP appendix
 9.1
 - Only considered as intercurrent medication if administered in the last 12 weeks before Week 36
 - Tetracyclines at the apeutic dose for at least 2 weeks:
 - Doses considered as therapeutic dose are specified in SAP appendix
 9.1
 - Only considered as intercurrent medication if administered in the last 10 weeks before Week 36
 - Very potent TCS with a weekly dose >20 g for 1 week:
 - Since the dose of TCS cannot be derived from the eCRF data, very potent TCS is considered as intercurrent medication when it is applied for 7 consecutive days or 14 days in total.
- 3.) Per protocol, death before week 36 is not considered as main intercurrent event in the efficacy analysis. It is added as main intercurrent event in this SAP.

[figure not shown]

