9.1.5 IV or IM corticosteroids

- administered (at least 1 administration, any dose) during the period from Week 28 to Week 36 (i.e., during the 8 week period required in the protocol to confirm the CRoff status)
 - or administered at any moment before Week 28 in any of the three following situations:
 - a) more than 60 mg/day of prednisone equivalent for 3 consecutive days (prednisone equivalent dose)
 - b) more than 40 mg/day of prednisone equivalent for 4 consecutive days (prednisone equivalent dose)
 - c) more than 7 days in total

SGS	Statistical Analysis Plan	
ARGX-113-2009	Final and Interim Analysis	Final 4.0 of 04NOV2024

 medications with ATC level2 = 'CORTICOSTEROIDS FOR SYSTEMIC USE' and cmroute='INTRAVENOUS' or 'INTRAMUSCULAR'

For NCOD, time-to-event analyses and endpoints that consider the period 'through Week 36' any administration of this type of medication is to be considered as an ICE, even if not during the period from Week 28 to Week 36. For these analyses, use the first day of the medication as start date of the ICE. For endpoints 'at Week 36', use the end of the 3, 4 or 8 (more than 7) days as start date of the ICE for situations a), b) and c) respectively.

9.1.6 Tetracyclines administered at least 100 mg/day for at least 2 weeks in total in the last 10 weeks before Week 36

medications with ATC level4 = 'TETRACYCLINES'

[figure not shown]
For NCOD, time-to-event analyses and endpoints that consider the period 'through Week 36' any episode of at least 2 weeks in total is to be considered as an ICE, even if not in the last 10 weeks before Week 36. For these analyses, use the end of the 2 weeks as start date of the ICE. For endpoints 'at Week 36', use the end of 2 weeks that fully fall in the last 10 weeks before Week 36 as start date of the ICE.

9.1.7 Any interventional study drug under development for BP given at any moment before Week 36

medications will be evaluated during the course of the study

9.1.8 Very potent TCS for 7 consecutive days or 14 days in total given at any moment before Week 36

• medications with ATC level4 = 'CORTICOSTEROIDS, VERY POTENT (GROUP IV)' and cmroute = 'TOPICAL' Use the end of the 7 or 14 days as start date of the ICE.

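### For the Part B primary endpoint the SAP narrows the protocol's any-time rule for immunosuppressants/dapsone and tetracyclines to late windows, without a stated reason and without a week-36 analysis under the protocol rule

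*SAP*

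**What the plan says.** **Protocol 9.3.2.** The estimand is confined to the confirmatory part: "The estimand framework for analysis of the primary endpoint applies only to part B of this study". The first main intercurrent event is "Intercurrent treatments before week 36". Its list includes "Immunosuppressants or dapsone at a therapeutic dose for at least 4 weeks" and "Tetracyclines at therapeutic dose for at least 2 weeks", neither with a look-back window. In the same list, the IV/IM corticosteroid item does have its own timing conditions. The strategy is composite, so a participant with such an event is a nonresponder.

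**SAP 4.1.2.1 and Appendix 9.1.** The body of the SAP repeats the list without windows and sends the derivation to the appendix. There the first class becomes "Immunosuppressants or dapsone at therapeutic doses for at least 4 weeks in total in the last 12 weeks before Week 36". For endpoints evaluated at week 36, which include the primary, the programmer is told to "use the end of 4 weeks that fully fall in the last 12 weeks before Week 36 as start date of the ICE". For tetracyclines (9.1.6) the instruction is to "use the end of 2 weeks that fully fall in the last 10 weeks before Week 36 as start date of the ICE". Both subsections keep the any-time rule for the normalized cumulative OCS dose (NCOD), for time-to-event analyses and for endpoints that run through week 36.

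**SAP 6.1.** The windows are listed among changes not covered by a protocol amendment, for example "Only considered as intercurrent medication if administered in the last 12 weeks before Week 36". They are presented as added detail. The topical corticosteroid change in the same list has a reason (the dose cannot be derived from the eCRF). The windows have none.

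**SAP 4.1.2.2 and 4.1.2.3.** The planned analyses of the week-36 proportion are:
- composite CMH on the full analysis set (FAS) and the per-protocol (PP) set;
- exact logistic regression;
- a non-linear model for the difference in proportions;
- a treatment-policy analysis with multiple imputation.

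**The concern.** The composite rule defines who is a responder in the confirmatory test. A window that drops earlier courses removes events that the protocol counts, so it changes the primary estimand and does more than add technical detail. If the protocol stands and the SAP departs from it, the report should let a reader see whether the Part B result holds under the protocol's definition. None of the analyses of the week-36 proportion does that. The composite analyses all use the narrowed rule, the PP analysis can remove such participants but does not rescore them, and the treatment-policy analysis ignores these events altogether.

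**Working it through.** The point is a comparison of text and rests on no figure stated in the plan. The arithmetic shows what the windows drop and how much a rescored participant could matter.

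**1. What the windows drop.** Week 36 is day 253 (SAP 2.2.4).
- Last 12 weeks: 253 − 84 = 169, so days 169 to 252. A continuous course from day 1 to day 195 has 195 − 169 + 1 = 27 days inside, fewer than 28, so it does not count. Ending on day 196 it has 28 and counts.
- Last 10 weeks: 253 − 70 = 183, so days 183 to 252. The same course has 195 − 183 + 1 = 13 days inside, fewer than 14, so it does not count. Ending on day 196 it has 14 and counts.
- The windows leave out weeks 0 to 24 (24/36 = 67% of treatment) and weeks 0 to 26 (26/36 = 72%).
- 12 = 8 + 4 and 10 = 8 + 2: the 8-week off-therapy period plus the minimum course.

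**2. Who is rescored.** Under the SAP, rescue therapy before week 36, stopping IMP for lack of efficacy, and death are already nonresponse (4.1.2.2). These intercurrent treatments exclude rescue use (3.4.2). What is left is a participant in CRoff at week 36 who had earlier non-rescue use: either prohibited use while on IMP (protocol 6.8.2), or use not recorded as rescue after stopping IMP for another reason. SAP 4.1 still treats the latter participants as receiving treatment. The documents give no count.

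**3. Which planned analyses use the any-time rule.** Time to CRoff (SAP 4.1.4, item 8) does. A participant with a main intercurrent event before CRoff is censored at or after the planned end of treatment, and the arms are compared by stratified log-rank on FAS. It does not test the week-36 proportion.

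**4. Size in the test.** Inputs: 120 participants randomized 1:1, so 60 per arm, and a 2-sided 5% level (protocol 9.5). The protocol's planning rates are redacted, so the SAP's illustrative 20% placebo and 50% efgartigimod (1.4.2.1) are used as an assumption. One participant is 1/60 = 1.7 points.

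The Mantel-Haenszel chi-square with one stratum and no continuity correction approximates the stratified CMH. With *a* efgartigimod and *c* placebo responders and *m* = *a* + *c*, it reduces to χ² = 119(*a* − *c*)² / [*m*(120 − *m*)].

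| Efgartigimod vs placebo | χ² | p |
|---|---|---|
| 30 vs 12 | 119·324/(42·78) = 11.77 | 0.0006 |
| 22 vs 12 | 119·100/(34·86) = 4.07 | 0.044 |
| 21 vs 12 | 119·81/(33·87) = 3.36 | 0.067 |
| 21 vs 11 | 119·100/(32·88) = 4.23 | 0.040 |

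With 12 placebo responders, 22 is the smallest significant efgartigimod count, and rescoring one efgartigimod responder loses significance. From 30 vs 12, eight rescored efgartigimod responders leave 22 vs 12 (still significant), and nine leave 21 vs 12 (not significant). The last row shows the opposite direction: from 21 vs 12, rescoring one placebo responder gains significance.

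**The case against.** The strongest reply has four parts.

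- **The change is disclosed and prespecified.** SAP 6.1 itemizes it, and protocol 9 leaves technical detail to a SAP finalized before database lock. This stands. A reader might infer a concealed change, and the documents do not support that.
- **The windows fit the endpoint.** Protocol 4.2.4.1 builds the primary endpoint on a definition that requires about two months off therapy, and the IV/IM corticosteroid rule is tied to the same 8-week period. A continuous course ending on day 195 stops 58 days before day 253, more than 8 weeks. This makes the motive plausible, but neither document states it, and the argument covers a single continuous course only.
- **The information is not lost.** A reader might infer that no planned test reveals the effect of the any-time rule. That goes too far: time to CRoff applies it inferentially. Tables 14.1.2.7 to 14.1.2.9 show concomitant, rescue and intercurrent therapies by arm, and Listings 16.2.4.4, 16.2.4.8 and 16.2.6.1 would allow individual rescoring. What remains is that the week-36 proportion itself is never tested under the protocol rule.
- **Materiality is not shown, and other SAP rules are stricter.** An event with missing dose or duration still counts, and death was added as a main intercurrent event. This is fair. The one-participant flip arises only for a result exactly at the threshold.

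**Conclusion.** The discrepancy is real and limited. For the Part B week-36 CRoff proportion, the SAP replaces the protocol's any-time rule for two drug classes with 12- and 10-week windows, gives no reason, and plans no analysis of that proportion under the protocol rule. A reader might infer that the primary analysis is wrong or favors efgartigimod. The documents support neither: the windows have a plausible clinical logic, and because early use could occur in either arm, the direction of any bias is unknown.

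The affected group should be small, since only early non-rescue use in a participant in CRoff at week 36 is scored differently, but its number cannot be known from the documents. At the assumed 30 vs 12 responders, nine efgartigimod responders and no placebo responders would have to be rescored to lose significance. At 22 vs 12, one would suffice. These figures rest on 60 per arm, the SAP's illustrative rates and an unstratified approximation. This is a minor improvement to the plan.

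**What to change.** In SAP 4.1.2.2 and 4.1.2.3, add one sensitivity analysis of the Part B primary endpoint: composite strategy, FAS, the same stratified CMH, with the protocol's any-time-before-week-36 rule for immunosuppressants/dapsone (at least 4 weeks) and tetracyclines (at least 2 weeks), and everything else unchanged. Add its table to the list in SAP 8.1. In SAP 6.1, state that the 12- and 10-week windows change the protocol 9.3.2 estimand for the primary endpoint, and give the reason.

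The cost is a few lines of text and one extra run on data already collected, using a definition the SAP already specifies for other endpoints. The primary analysis does not change. The downside is one more table to report, in which a few more participants may count as nonresponders.

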9.1.5 IV or IM corticosteroids

- administered (at least 1 administration, any dose) during the period from Week 28 to Week 36 (i.e., during the 8 week period required in the protocol to confirm the CRoff status)
 - or administered at any moment before Week 28 in any of the three following situations:
 - a) more than 60 mg/day of prednisone equivalent for 3 consecutive days (prednisone equivalent dose)
 - b) more than 40 mg/day of prednisone equivalent for 4 consecutive days (prednisone equivalent dose)
 - c) more than 7 days in total

SGS	Statistical Analysis Plan	
ARGX-113-2009	Final and Interim Analysis	Final 4.0 of 04NOV2024

 medications with ATC level2 = 'CORTICOSTEROIDS FOR SYSTEMIC USE' and cmroute='INTRAVENOUS' or 'INTRAMUSCULAR'

For NCOD, time-to-event analyses and endpoints that consider the period 'through Week 36' any administration of this type of medication is to be considered as an ICE, even if not during the period from Week 28 to Week 36. For these analyses, use the first day of the medication as start date of the ICE. For endpoints 'at Week 36', use the end of the 3, 4 or 8 (more than 7) days as start date of the ICE for situations a), b) and c) respectively.

9.1.6 Tetracyclines administered at least 100 mg/day for at least 2 weeks in total in the last 10 weeks before Week 36

medications with ATC level4 = 'TETRACYCLINES'

[figure not shown]
For NCOD, time-to-event analyses and endpoints that consider the period 'through Week 36' any episode of at least 2 weeks in total is to be considered as an ICE, even if not in the last 10 weeks before Week 36. For these analyses, use the end of the 2 weeks as start date of the ICE. For endpoints 'at Week 36', use the end of 2 weeks that fully fall in the last 10 weeks before Week 36 as start date of the ICE.

9.1.7 Any interventional study drug under development for BP given at any moment before Week 36

medications will be evaluated during the course of the study

9.1.8 Very potent TCS for 7 consecutive days or 14 days in total given at any moment before Week 36

• medications with ATC level4 = 'CORTICOSTEROIDS, VERY POTENT (GROUP IV)' and cmroute = 'TOPICAL' Use the end of the 7 or 14 days as start date of the ICE.

9.2 GTI: DERIVATION OF CWS AND AIS

9.2.1 Allocate weights

Weights per item are attributed as specified below. GTI at Wx is evaluated versus previous GTI assessment. The first time point is referred to as *start (or previous)* and the second time point within each comparison is referred to as *follow-up (or current)*.

Increase, decrease or no change in medication intake compared to previous assessment are checked in the GTI assessment. A missing evaluation, including for external data, will be considered as no change with weight=0.

External GTI data (i.e., LDL/HbA1c/BP and BMI) are allocated to a GTI assessment based on dates. The last available value of these external data since previous GTI assessment will be used.

Changes from severe to moderate do not have any impact on calculation of CWS/AIS. Severe outcome on an item however is captured on the specific list (SL).

9.2.1.1 BMI (COMPARED TO PREVIOUS ASSESSMENT)

•	Moderate decrease in the direction of the normal range [<25 kg/ m2] by at least 5 BMI units	-36
•	Minor decrease in the direction of the normal range [<25 kg/ m2] by more than 2 but less than 5 BMI units	-21
•	No significant change (BMI remains within +/- 2 BMI units compared with start) OR BMI remains <25 kg/ m2	0
•	Minor increase in BMI (increase by more than 2 but less than 5 BMI units,	
	to above the upper limit of normal BMI [≥25kg/m2])	21
•	Moderate increase in BMI (increase by at least 5 BMI units above normal BMI [≥25kg/m2])	36

SGS	Statistical Analysis Plan	
ARGX-113-2009	Final and Interim Analysis	Final 4.0 of 04NOV2024

9.2.1.2 GLUCOSE TOLERANCE (COMPARED TO PREVIOUS ASSESSMENT)

Moderate improvement in glucose tolerance:

-44

- o HbA1c declined >10% from start AND medication decrease
- Minor improvement in glucose tolerance:

-32

- o HbA1c declined >10% from start AND no medication increase (unchanged or missing) AND start HbA1c ≥ 5.7
- o HbA1c within 10% of start AND decrease in diabetic medication
- o HbA1c < 5.7 AND decrease in diabetic medication AND HbA1c increased >10%
- No significant change in glucose tolerance:

0

- o HbA1c within 10% of start or (start and follow-up) HbA1c < 5.7 AND no change in medication (or missing)
- o HbA1c increased > 10% of start AND a decrease in medication AND follow-up HbA1c ≥ 5.7
- o HbA1c decreased by > 10% of start AND an increase in medication
- Minor worsening of glucose tolerance or medication status:

32

- o HbA1c increased >10% of start AND no change in medication (or missing) AND follow-up HbA1c ≥ 5.7%
- o HbA1c within 10% of start AND increase in diabetic medication
- Moderate worsening of glucose tolerance despite increased diabetic treatment: 44
 - o HbA1c increased >10% of start AND an increase in diabetic medication AND follow-up HbA1c ≥ 5.7%

Note: changes in medication for glucose control, used in the above weight derivations, are assessed as a GTI specific question.

SGS	Statistical Analysis Plan	
ARGX-113-2009	Final and Interim Analysis	Final 4.0 of 04NOV2024

9.2.1.3 Blood Pressure (compared to previous assessment)

Moderate improvement in BP:

- -44
- Decrease in either systolic or diastolic BP of >10% of start AND medication decrease AND start systolic BP ≥120 mmHg or start diastolic BP ≥ 85 mmHg
- Minor improvement in BP:

-19

- Decrease in either systolic or diastolic BP of >10% of start AND no medication increase (unchanged or missing) AND start systolic BP ≥120 mmHg or start diastolic BP ≥ 85 mmHg
- o Systolic AND diastolic BP within 10% of start AND a decrease in medication
- Systolic BP < 120 and diastolic BP < 85 (both start and end) AND a decrease in medication
- No significant change in BP:

0

- Systolic AND diastolic BP within 10% of start or (start and follow-up) systolic / diastolic BP < 120/85 resp AND no change in medication (or missing)
- Increase in systolic or diastolic BP >10% of start AND a decrease in medication AND follow-up systolic BP ≥120 mmHg or diastolic BP ≥ 85 mmHg
- Decrease in systolic or diastolic BP of > 10% of start AND an increase in medication AND start systolic BP ≥120 mmHg or diastolic BP ≥ 85 mmHg
- Minor worsening of BP:

19

- Increase in systolic or diastolic BP >10% of start AND no change in medication (or missing) AND follow-up systolic BP ≥120 mmHg or diastolic BP ≥ 85 mmHg
- o Systolic AND diastolic BP within 10% of start AND an increase in medication
- O Systolic BP < 120 and diastolic BP < 85 (both start and end) AND an increase in medication
- Moderate worsening of BP despite treatment

44

 Increase in systolic or diastolic BP >10% of start AND an increase in medication AND follow-up systolic BP ≥120 mmHg or diastolic BP ≥ 85 mmHg

SGS	Statistical Analysis Plan	
ARGX-113-2009	Final and Interim Analysis	Final 4.0 of 04NOV2024

Notes:

- 1. changes in medication for BP control, used in the above weight derivations, are assessed as a GTI specific question.
- 2. check \geq normal range and > 10% needs to be done separately for systolic and diastolic BP. In case of both an increase and decrease occurs, this is considered as no change in BP and the score will be based on the change in medication (score = \pm 19 for increase/decrease, score = 0 for no change).
- 3. Hypertensive Emergency = Y or PRES = Y at current visit is provided a score 44 regardless of the value at previous visit

SGS	Statistical Analysis Plan	
ARGX-113-2009	Final and Interim Analysis	Final 4.0 of 04NOV2024

